7.2 Phase 1B and Phase 2: UTSW

In compliance with the Simmons Cancer Center Data and Safety Monitoring Committee, the Principal Investigator will provide a Data and Safety Monitoring (DSM) report to the Simmons Cancer Center Data and Safety Monitoring Committee (DSMC) semi-annually beginning six months after accrual has opened (if at least one patient has been enrolled) or one year after accrual has opened (if no patients have been enrolled at the six-month mark).

The Principal Investigator will review all patient data at least every 6 months, and provide a semi-annual report to the DSMC. This report will include:

- HRPP protocol number, protocol title, Principal Investigator name, data coordinator name, regulatory coordinator name, and statistician name
- Date of initial HRPP approval, date of most recent consent HRPP approval/revision, date of HRPP expiration, date of most recent QA audit, study status, and phase of study
- History of study including summary of substantive amendments; summary of accrual suspensions including start/stop dates and reason; and summary of protocol exceptions, error, or breach of confidentiality including start/stop dates and reason
- Study-wide target accrual and study-wide actual accrual
- Protocol activation date
- Average rate of accrual observed in year 1, year 2, and subsequent years
- Expected accrual end date and accrual by cohort
- Objectives of protocol with supporting data and list the number of participants who have met each objective
- Early stopping rules with supporting data and list the number of participants who have met the early stopping rules

- Summary of toxicities separated by cohorts with the number of dose-limiting toxicities indicated
- Abstract submissions/publications
- Summary of any recent literature that may affect the safety or ethics of the study

The study principal investigator and Research Study Coordinator will monitor for serious toxicities on an ongoing basis. Once the principal investigator or Research Study Coordinator becomes aware of an adverse event, the AE will be reported to the HRPP and DSMC according to institutional guidelines.

8.0 STATISTICAL CONSIDERATIONS

8.1 Study Design

A rolling six design which is intended for relatively safe trials and shortening the study duration is proposed for the phase 1 portion ⁷⁴. In the rolling six design, three to six patients can be enrolled to a dose each time. The dose de-escalation occurs when two or more DLT occur at a dose level while dose escalation occurs when 3/3, 4/4, 5/5, 5/6 or 6/6 patients are evaluated without DLT ⁷⁵. Three dose levels will be tested in the phase 1 study, 0.05, 0.075 and 0.10 mg/kg. LS301 will be administered intravenously at a starting dose of 0.05 mg/kg to a cohort of six patients and escalate/de-escalate following the decision rule of the rolling six design. Once six patients have been included at the current dose level, inclusions are suspended until at least five of the six patients have completed the procedure without DLT observed in the evaluation period. MTD is hit where two or more patients out of six at a dose level experience DLT. We do not expect any serious adverse events related to LS301 at the initial Dose Level 1. Once the MTD is determined, an expansion cohort with 9 patients will be tested at the MTD and an optimal imaging dose will be recommended for the subsequent phase 2 trial.

At the completion of the expansion cohort, a single arm phase 2 trial will be performed at the optimal imaging dose. A breast surgeon will perform breast conserving surgery per standard of care. At the completion of the surgery, a second investigator (to reduce bias in data collection) will wear the cancer vision goggle (CVG) to visualize the excised tissue to determine if there are any positive margins based on the presence of LS301 fluorescence. If any positive margins are observed, the subject will be considered to have a positive margin; otherwise, the margin is considered negative. The excised tissue will later be examined by a breast cancer pathologist. Standard pathologic techniques will be used to determine if there are positive margins. Particular attention will be paid to the sites marked following CVG assessment to confirm whether the margin is positive or negative at any of these sites, or positive at other locations not identified by CVG. No interventions will be allowed based on the CVG results.

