1.10 Clinical Study Plan

The primary goal of this human pilot study is to translate the novel imaging agent LS301, which selectively identifies breast cancer cells with high accuracy, to human patients. Diverse animal models of breast cancer have been investigated to surgical removal of spontaneous, disseminated, and diffuse tumors, which were detected to single cancer cell level by LS301. We have also shown that the NIR fluorescence can be captured efficiently using CVG.

The maximum recommended starting dose (MRSD) for this clinical trial was based on the NOAEL from animal studies. As shown in the GLP toxicology document, the NOAEL from the rat toxicity study is 10 mg/kg for females and 0.5 mg/kg for male rats, which is equivalent to human equivalent dose (HED) of 1.6 mg/kg and 0.081 mg/kg, respectively. Applying a safety margin (typically 10-fold) to the NOAEL gives MRSD of 0.16 mg/kg based on female NOAEL and 0.0081 mg/kg based on the NOAEL in male rats. The highest non-severely toxic dose (HNSTD) in the rat toxicity study was determined to be 10 mg/kg (HED 1.6 mg/kg) in both male and female rats. Another approach that is considered appropriate to determine a safe starting dose is using 1/6th of the HNSTD in a more sensitive species. Based on the NOAEL and HNSTD from the rat toxicity study, the maximum recommended safe dose to test in the FIH study was estimated to be between 0.16 and 0.26 mg/kg. While previous investigations with LS301 in mice showed the lowest detectable dose with the CVG to be 0.075 mg/kg (equivalent to HED of 0.006 mg/kg), an anticipated optimal starting dose of 0.1 mg/kg will be used as the starting dose in the clinical study. This dose is well within the estimated range for the MRSD estimated from the rat toxicity study.

We propose a phase 1 rolling six dose-escalating design given that this is the first-in-human use of LS301, followed by a phase 2 trial for preliminary evaluation of its diagnostic capabilities (including sensitivity and specificity). During phase 1, LS301 will be administered intravenously to a cohort of six patients at a dose of 0.05 mg/kg; if fewer than 2 DLTs are observed, LS301 will be given at the next high dose level of 0.075 mg/kg; if fewer than 2 DLTs are observed, LS301 will be given at the expected optimal dose of 0.1 mg/kg. Once safety is confirmed and the optimal imaging dose is established, an additional 9 patients will be enrolled in the phase 1 expansion cohort to evaluate for safety.

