5.2.1.1 Dose Escalation Schema

LS301 Dose Level	LS301 Dose
Level 1 (starting dose)	0.05 mg/kg
Level 2	0.075 mg/kg
Level 3	0.1 mg/kg

Dose escalation may occur as soon as the last patient in a cohort has completed her one-hour post-injection toxicity monitoring.

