5.2.1.3 Definition of Dose-Limiting Toxicities

DLT is defined as any grade 2 or above toxicity that occurs during the hour after injection that is considered possibly, probably, or definitely related to LS301.

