5.2.1.4 Dose Escalation Criteria

The molecular probe LS301 is an imaging agent binding to breast cancer cells and other malignant cells and will be visualized through by CVG which is a non-significant risk device. Similar to the FDA-approved agent ICG, we do not expect any serious adverse events caused by the agent.

A rolling six design will be used for the phase 1 portion. In the rolling six design, 2 to 6 patients can be enrolled to a dose each time. The dose de-escalation occurs when two or more DLTs occur at a dose level, while dose escalation occurs with 3/3, 4/4, 5/5, 5/6, or 6/6 patients are evaluated without DLT. (Refer to Section 8.1 for further details.)

5.2.2 Phase 2

After data from the phase 1 portion of the study have been submitted to and reviewed by the FDA, and if analysis of the data from phase 1 confirms the safety of administering LS301 in humans and establishes the optimal imaging dose, 88 patients will be enrolled in the phase 2 portion of the study after any necessary protocol revisions have been made based on phase 1 data and FDA approval.

It is expected that the study procedures for phase 2 will be the same as the procedures in phase 1. The optimal imaging dose of LS301 determined in phase 1 will be administered in phase 2.

The breast tissue and axillary LNs will be imaged non-invasively using the CVG and worn by a non-operating member of the surgical team. After removal of the breast cancer and SLNs using current best practice, a member of the surgical team who is not conducting the surgery will wear the CVG to determine if LS301 fluorescence is present at the margin and in SLNs, using a global threshold of 20% signal above background or a dynamic statistical threshold to indicate a positive margin. The accuracy of determining margin positivity will be established by comparing the CVG assessment to histopathology.

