5.4.2 Clinical Laboratory Testing

Laboratory tests will consist of the following: standard CBC, comprehensive metabolic panel and urinalysis obtained at the following time points:

- Baseline: within 30 minutes prior to injection of LS301
- 60 minutes after injection of LS301
- Approximately one hour prior to surgery

Approximately 14 ml of blood and a urine sample will be collected at each time point. For patients enrolled in phase 1B and phase 2 of the study, a portion of the blood samples from each time point will be used to identify the predominant blood protein(s) that binds LS301 and mediates the bioavailability of the agent (refer to Section 5.6). Phase 1B refers to phase 1 study after completing drug safety and selecting optimal dose for testing at 2 and 4 hours from injection to surgery. The current project is that if 3 patients at each of the 3 dose level do not experience adverse events, we will need only 9 patients for the drug safety study (phase 1A) and additional 9 patients at the selected dose for testing at 2, 4, and >12 hours (3 patients for each time point) from injection to surgery.

The results of standard of care laboratory testing obtained up to 30 days post injection will be reviewed. Analysis of this will take into account that the subject has undergone surgical removal of tumor and neoadjuvant treatment including hormonal therapy or chemotherapy.

The following changes from baseline clinical laboratory values are considered to be noteworthy and require assessment as to clinical significance when they fall outside of normal limits. Clinically significant changes in laboratory values should be followed up daily until they return to baseline or normal levels, or until follow-up is no longer warranted. Laboratory values that are abnormal at baseline but move into normal range will not be considered clinically significant. If a clinically significant change of a laboratory value is noted, it will be reported on the AE log.

Analyte	Change from baseline
Hemoglobin	> 2g/dL
WBCs	> 1 K/mm ³
Neutrophils	> 10 %
Lymphocytes	> 10%
Platelets	> 50 K/mm ³
Creatinine	> 0.75 mg/dL
BUN	> 20 mg/dL
Calcium	> 1mg/dL
Sodium	> 5 mmol/L
Potassium	> 0.5 mmol/L
CO ₂	> 4 mmol/L
ALT (SGPT)	> 150 IU/L
AST (SGOT)	> 100 IU/L
Alkaline Phosphatase	> 150 IU/L
Total Bilirubin	> 0.5 mg/dL
Albumin	> 1g/dL

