5.9 Duration of Study Participation

If at any time the constraints of this protocol are considered to be detrimental to the patient's health and/or the patient no longer wishes to continue in the protocol, the patient should be removed from the study and the reason for discontinuation documented in the case report forms.

Patients will be on study for the duration of the screening process and the surgery or until one of the following criteria applies:

- Death
- Adverse event(s) that, in the judgment of the investigator, may cause severe or permanent harm
- Suspected pregnancy
- Serious noncompliance with the study protocol
- Lost to follow-up
- Patient withdraws consent
- Investigator removes the patient from study
- The Siteman Cancer Center decides to close the study for phase 1A
- The UTSW Department of Surgery or Simmons Comprehensive Cancer Center to close the study for phase 1B and phase 2

Follow-up will continue for 30 days post-surgery (for collection of follow-up lab data).

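### Phase 1A escalation counts DLTs regardless of grade, so one fatal or life-threatening reaction with five DLT-free patients still permits the next dose, and the protocol states no mandatory hold

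*Combined protocol and SAP*

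**What the plan says.** Every dose decision in phase 1A is a count of DLTs.

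- **What counts.** Section 5.2.1.3: "DLT is defined as any grade 2 or above toxicity that occurs during the hour after injection", provided it is at least possibly related to LS301. Grades 2 to 5 carry equal weight.
- **Escalation.** Section 8.1: "dose escalation occurs when 3/3, 4/4, 5/5, 5/6 or 6/6 patients are evaluated without DLT". Section 5.2.1.4 has the same rule ("dose escalation occurs with 3/3, 4/4, 5/5, 5/6, or 6/6 patients are evaluated without DLT"). Section 1.10 is firmer: "if fewer than 2 DLTs are observed, LS301 will be given at the next high dose level of 0.075 mg/kg", with the same condition for the step to 0.1 mg/kg.
- **Suspension.** The only accrual suspension in the dose rules applies once six patients are in at a level. Under Section 8.1, "inclusions are suspended until at least five of the six patients have completed the procedure without DLT observed in the evaluation period".
- **Early stop.** Section 8.5 stops phase 1 if two of six patients at dose level 1 have a DLT.
- **Timing.** Section 5.2.1.1: "Dose escalation may occur as soon as the last patient in a cohort has completed her one-hour post-injection toxicity monitoring".

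Other sections deal with serious events outside the dose rules. Section 7.1 has the principal investigator and the coordinator watch for serious toxicity continuously and report adverse events to HRPO and QASMC. Section 6.1.2 has QASMC told of unanticipated problems once HRPO has acknowledged them. Section 6.1.3 gives 7 calendar days for the FDA report of an unexpected fatal or life-threatening suspected reaction. Appendix B gives HRPO 1 working day where an unanticipated problem results in a death. Section 5.9 lists among the end-of-participation criteria: "The Siteman Cancer Center decides to close the study for phase 1A".

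**The concern.** LS301 is being given to humans for the first time. It is an imaging agent, and its images may not change the operation, so a participant gets no treatment benefit to set against harm. The plan expects no serious adverse events. One related death or life-threatening reaction would contradict that expectation, and most investigators would want it reviewed before anyone received a higher dose. The written rule points the other way: if the other five patients at the level are DLT-free, the next dose is permitted, and no step in the protocol requires a committee to agree first. The shortest reporting limit is 1 working day, whereas escalation may follow one hour after the last injection in the cohort. A fatal reaction after the first hour is not a DLT at all, so it does not enter the count.

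**Working it through.** **1. The plan's own DLT figures.** Section 8.4 tabulates the chance of at least 3 DLTs in the 9 expansion patients. The exact binomial gives 0.0084 at a true rate of 5% and 0.910 at 50%, as printed. The 1% row computes to 0.000080 against a printed 0.000084, which is immaterial. The table covers the expansion cohort only. The plan gives no operating characteristics for the phase 1A rules.

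**2. Rule logic.** Take one related fatal or life-threatening reaction within the hour and five DLT-free patients at the same level.

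| Rule | Condition | Result |
|---|---|---|
| Escalate (5.2.1.4, 8.1) | 5/6 DLT-free | Met |
| Escalate (1.10) | 0 or 1 DLT | Met |
| Suspension (8.1) | Lifts at 5 of 6 DLT-free | Lifted |
| De-escalate (8.1) | At least 2 DLTs | Not met |
| Early stop (8.5) | 2 of 6 DLTs at level 1 | Not met |

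**3. Size, given that a severe event has occurred.** Suppose one of the first three patients at a level has a severe reaction. Escalation then needs the other five to be DLT-free. With total DLT rate d and independent patients, the probability is (1 − d)^5. At the rates tabulated in Section 8.4:

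| d | 1% | 5% | 10% | 20% | 30% | 40% | 50% |
|---|---|---|---|---|---|---|---|
| (1 − d)^5 | 95.1% | 77.4% | 59.0% | 32.8% | 16.8% | 7.8% | 3.1% |

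This holds whether levels fill to six or escalate at 3/3, because a DLT among the first three removes the 3/3 route.

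**4. Unconditional size, illustrative only.** The documents give no severe-event rate. Let q be the assumed rate of fatal or life-threatening related reactions in the hour, p = 10% the assumed rate of other DLTs, and n = 1 − p − q. Let E be the chance per level of escalating with one severe event, and C the chance of escalating with none. Two escalation steps give E + C × E.

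- Fill to six (1.10, 8.1): E = 6q·n^5 and C = n^6 + 6p·n^5.
- 3/3 path, as projected in Section 5.4.2 ("if 3 patients at each of the 3 dose level do not experience adverse events, we will need only 9 patients"): E = 3q·n^5 and C = n^3 + 3p·n^5.

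| q | Path | E | C | Two steps |
|---|---|---|---|---|
| 0.1% | Fill to six | 0.0035 | 0.880 | 0.66% |
| 0.1% | 3/3 | 0.0018 | 0.903 | 0.34% |
| 1% | Fill to six | 0.0335 | 0.832 | 6.1% |
| 1% | 3/3 | 0.0168 | 0.872 | 3.1% |

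**5. How often a single-event hold would be used.** Let t be the chance of a severe event at a level. A later level is reached only if the earlier one escalates, so over three levels the chance of at least one hold is t(1 + C + C²). This counts reactions in the DLT hour only.

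- Fill to six: t = 1 − (1 − q)^6. At q = 0.1%, 0.00599 × 2.655 = 1.6%. At q = 1%, 0.0585 × 2.524 = 14.8%.
- 3/3 path, with three more patients after exactly one DLT in the first three: t = [1 − (1 − q)^3](1 + 3p·n²). At q = 0.1%, 0.00372 × 2.718 = 1.0%. At q = 1%, 0.0368 × 2.634 = 9.7%.

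Stopping dosing at the second DLT within a level lowers these slightly. In round terms the hold is used in 1% to 1.6% of trials at q = 0.1% and in about 9% to 15% at q = 1%.

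**The case against.** The strongest reply is that this is the design working as chosen. Rolling six counts DLTs without regard to grade, and the plan says the design suits trials expected to be relatively safe. The DLT threshold is low, so a severe reaction plus one possibly related grade 2 event at the same level blocks escalation. A DLT in the first three patients means five DLT-free patients are needed at the same dose. The dose steps are modest (0.075/0.05 = 1.5-fold and 0.1/0.075 = 1.33-fold). Section 7.1 already sends adverse events to QASMC without mentioning HRPO acknowledgement, and its reports must list accrual suspensions, so pauses are foreseen. All of this stands. It limits the force of the point but does not supply a hold.

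A reader might infer three stronger claims that the documents do not support.

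- **That the protocol compels a higher dose after a death.** Sections 1.10 and 8.1 are worded firmly, but Section 5.2.1.1 is permissive, and the investigator, IRB or FDA could pause the trial.
- **That nobody would review such an event.** Phase 1A also runs under Washington University's monitoring plan and IRB policies. These are not supplied and may contain a hold.
- **That rolling six has been misapplied, or that the scenario is likely.** Neither follows. The rule is applied as chosen, and the conditional figures say nothing about how often a severe reaction occurs.

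Section 5.2.1 describes cohort 1 partly in the past tense, so level 1 may already have been dosed. The current text still states the rule.

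**Conclusion.** The gap is real, and its remedy is a cheap safety improvement to a chosen design. Read as written, the phase 1A rules permit escalation after one related fatal or life-threatening reaction with five DLT-free patients, and no provision in the protocol requires a hold. That conclusion is rule logic and needs no assumed rate.

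The most dependable size is conditional: 77.4% at a 5% DLT rate and 59.0% at 10%, assuming independent patients with a common rate. The unconditional range of about 0.3% to 6% over two escalation steps depends on assumed p and q and only illustrates. If q is near 0.1% the event is rare, and the case for the hold then rests on the gravity of the consequence and the low cost of preventing it. Confidence is medium, because institutional policies outside the documents may already provide the hold.

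**What to change.** Add to Section 8.5: any single fatal or life-threatening suspected adverse reaction (Appendix A definitions) that the study team becomes aware of in phase 1A, whether or not it falls in the one-hour DLT window, suspends enrolment and escalation until QASMC has reviewed it and agreed to resume. Tying the hold to awareness matters because Section 6.0 tracks adverse events for one hour only.

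State in Sections 6.1.2 and 7.1 that the report to QASMC for such an event does not wait for HRPO acknowledgement. Make the escalation text in Sections 1.10, 5.2.1.1, 5.2.1.4 and 8.1, including the suspension sentence in 8.1, subject to this hold.

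The cost is one rule, short cross-references and a resume decision by an existing committee. No extra patients or new committee are needed. The downside is an enrolment pause if such an event occurs, with the frequencies shown in step 5 of the working under the stated assumptions.

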5.2.1.2 Definition of Optimal Dose

The optimal dose will be the dose at which fewer than 2 DLTs are observed and optimal image quality is observed. It need not be the maximum tolerated dose if optimal image quality is observed at a lower dose than the MTD.

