8.5 Early stopping rule

We don't expect any toxicities for LS301 but grade 1 toxicity is usually acceptable for imaging agent. As such, the trial will stop early in the phase 1 part following the rolling six design rule if dose level 1 has two out of six patients experience DLTs.

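### Section 8.1 calls a level with two or more DLTs in six the MTD and sends the nine expansion patients there, against the plan's own de-escalation, stopping and optimal-dose rules

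*Combined protocol and SAP*

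**What the plan says.** Section 8.1 sets out the rolling six design for three levels (0.05, 0.075 and 0.10 mg/kg). On the MTD it says "MTD is hit where two or more patients out of six at a dose level experience DLT", and on the expansion "Once the MTD is determined, an expansion cohort with 9 patients will be tested at the MTD". It has the optimal imaging dose recommended for phase 2 in connection with that expansion.

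Other statements bear on the same decision:

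- **8.1, same paragraph:** "The dose de-escalation occurs when two or more DLT occur at a dose level". After the sixth patient at a level, enrolment is held until five or more of the six have finished free of DLT.
- **5.2.1.4:** "The dose de-escalation occurs when two or more DLTs occur at a dose level".
- **8.5:** the trial stops in phase 1 "if dose level 1 has two out of six patients experience DLTs".
- **5.2.1.2:** "The optimal dose will be the dose at which fewer than 2 DLTs are observed and optimal image quality is observed". It adds: "It need not be the maximum tolerated dose if optimal image quality is observed at a lower dose than the MTD".
- **1.10:** "Once safety is confirmed and the optimal imaging dose is established, an additional 9 patients will be enrolled". Section 5.2.1 likewise starts the expansion once the optimal dose is known, and 5.4.2 puts the nine patients at the selected dose.

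**The concern.** In ordinary use the MTD is the highest dose that was tolerated. Section 8.1 attaches the term to a dose that failed the tolerability rule and then assigns nine more patients to it. Section 5.2.1.2 uses the term in the ordinary sense, because it treats the MTD as a dose that could itself be optimal. That is impossible under the 8.1 wording.

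What is at stake is a dose-assignment rule in a first-in-human study. Sections 5.2.1 and 5.2.1.4 both refer the reader to 8.1 for the design, and phase 1B runs at a different institution from phase 1A. The expansion site therefore depends on the written rule. Read alone, 8.1 also names no expansion dose if no level reaches two DLTs, although the sponsor expects no toxicities (8.5).

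**Working it through.** **1. The rules applied to each possible outcome**

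| Outcome of escalation | 8.1, MTD and expansion sentences | Rest of the plan |
|---|---|---|
| Two or more DLTs in six at level 2 or 3 | That level is the MTD; nine more patients go there | De-escalate (8.1, 5.2.1.4). Enrolment hold cannot lift: at most 6 − 2 = 4 finish without DLT, and five are needed (8.1). Level cannot be optimal (5.2.1.2) |
| Two DLTs in six at level 1 | 0.05 mg/kg is the MTD; nine more patients go there | Trial stops (8.5) |
| No level reaches two DLTs | No MTD, so no expansion dose | Expansion at the optimal or selected dose (1.10, 5.2.1, 5.4.2) |

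The two 8.1 sentences disagree with the rest of the plan in the first two rows and give no answer in the third. No section says that the level below the one with two DLTs is meant.

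**2. The plan's own figures for the expansion cohort**

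Section 8.4 tabulates the probability of at least 33% DLTs in nine patients, that is, three or more. The formula is P(X ≥ 3) = 1 − Σ C(9,k) p^k (1−p)^(9−k), summed over k = 0, 1, 2.

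| True DLT rate | Stated | Recomputed |
|---|---|---|
| 1% | 0.000084 | 0.0000803 |
| 5% | 0.0084 | 0.00836 |
| 10% | 0.053 | 0.0530 |
| 20% | 0.262 | 0.2618 |
| 30% | 0.537 | 0.5372 |
| 40% | 0.768 | 0.7682 |
| 50% | 0.91 | 0.9102 |

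The table reproduces. The 1% entry equals the leading term 84p³, an immaterial difference. None of these figures depends on how the MTD is defined.

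**3. Size if 8.1 is followed literally**

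The lowest observed rate that 8.1 accepts for its MTD is 2/6 (33%). The highest that a rule of fewer than two in six accepts is 1/6 (17%). Taking these as true rates, purely as an illustration:

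- expected DLTs in nine patients: 9 × 1/3 = 3.0, against 9 × 1/6 = 1.5;
- P(three or more of nine): 0.62, against 0.18.

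An observed 2/6 does not establish a rate of 1/3: its exact (Clopper-Pearson) 95% interval is 4.3% to 77.7%.

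**4. Chance that 8.1 names no MTD**

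Assume six patients at each of three levels and the same true rate p at each. Then P(no level reaches two DLTs) = [(1−p)^6 + 6p(1−p)^5]³.

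| Assumed p | P(0 or 1 DLT in six) | Cubed |
|---|---|---|
| 1% | 0.9415 + 0.0571 = 0.9985 | 0.996 |
| 5% | 0.7351 + 0.2321 = 0.9672 | 0.905 |
| 10% | 0.5314 + 0.3543 = 0.8857 | 0.695 |

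Treating fewer than six at a level, which the escalation rule allows, can only raise these probabilities.

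**The case against.** The best defence is that nobody reading the whole plan would be misled. The 8.1 paragraph itself orders de-escalation and holds enrolment, so it contains two instructions against adding patients at a level with two DLTs. Section 8.5 settles level 1. Three other sections state the expansion dose correctly, and 5.2.1.2 bars any level with two DLTs from being optimal. Section 5.4.2 covers the case without adverse events, so the missing MTD is a gap only when 8.1 is read in isolation. The phase 1 objective in 2.1 is safety and an optimal imaging dose, not an MTD. A DLT here starts at grade 2 within an hour of injection, so a DLT need not be severe.

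Much of this stands, and it limits the practical risk. It does not remove the error. The de-escalation and hold rules in 8.1 conflict with its expansion sentence; they do not say which prevails. *Hit* may be loose wording for *exceeded*, but no text says so, and the procedures sections send the reader to 8.1. The probabilities in step 4 describe 8.1 taken alone, not the plan as a whole. It is also fair that recording the MTD as not reached would serve as well as naming level 3.

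**Conclusion.** The concern holds. Two sentences in 8.1 are wrong as written and conflict with the de-escalation and enrolment-hold rules in the same paragraph and with 5.2.1.4, 5.2.1.2 and, at level 1, 8.5. Section 8.1 is the outlier; 1.10, 5.2.1 and 5.4.2 already give the right expansion dose.

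The exposure is nine phase 1B patients if 8.1 is applied literally after two DLTs at a level. If LS301 is as safe as expected, the likelier consequence is that 8.1 supplies no MTD. Sample size, power and the 8.4 table are unaffected. All true DLT rates used here are assumptions, and the probabilities in step 4 also assume six patients per level and a common rate. The contradiction rests on the text alone. It should be fixed because it concerns dose assignment in a first-in-human study.

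**What to change.** Amend 8.1 to state:

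1. Two or more DLTs in up to six patients at a level means that the MTD has been exceeded.
2. The MTD is the highest tested level with fewer than two DLTs. If no level reaches two, it is level 3 (0.1 mg/kg); the sponsor may prefer to record it as not reached.
3. Two DLTs at level 1 stop the trial under 8.5, with no expansion.
4. The nine expansion patients receive the optimal imaging dose as defined in 5.2.1.2, at or below the MTD, chosen before the expansion and confirmed for phase 2 after it.

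The sponsor should also say how many patients must have been treated at a lower level before it is declared the MTD, since escalation is allowed after three.

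The conflict itself is cured by rewording two sentences, with no added patients, procedures or analyses. A minimum number at the lower level could add a few patients there after de-escalation, if the sponsor chooses to set one.
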